2. LIST OF ABBREVIATIONS

Abbreviation	Term
APTT	Activated Partial Thromboplastin Time
AE	Adverse Event
CI	Confidence Interval
CRA	Clinical Research Associate
CRF	Case Report Form DM
	Data Management
DNA	Deoxyribonucleic acid
DTI	Direct Thrombin Inhibitor
DVT	Deep Vein Thrombosis
GCP	Good Clinical Practices
IRB/IEC	Institutional Review Board/Independent Ethics Committee
ICH	International Conference on Harmonization
ICF	Informed Consent Form
IMP	Investigational Medicinal Product
INR	International Normalized Ratio
PE	Pulmonary Embolism
RB	Recombinant Bacteria
S.A.E.	Serious Adverse Event
VTE	Venous Thromboembolism

4. INTRODUCTION

4.1. Background

Hirudin is the most potent naturally-occurring direct thrombin inhibitor (DTI), and the first parenteral anticoagulant used on humans.¹

Originally derived from the medicinal leech (*Hirudo medicinalis*), it consists of a 65 amino acids polypeptide chain, forming non-covalent, equimolar, non-reversible 1:1 complexes with α thrombin.¹ When hirudin-bound, thrombin-catalyzed reactions and fibrinogen clotting are blocked, and coagulation is subsequently inhibited.² Hirudin was previously produced in limited amounts, however, recombinant DNA technology allowed its mass production.³ These recombinant forms bind bivalent to thrombin with pharmacokinetic and anticoagulant profile similar to that of the native form.⁴

Recombinant Hirudin is a direct inhibitor of thrombin. It binds in 1:1 ratio with thrombin thus blocking the coagulation cascade and the formation of thrombi.⁵

Unlike heparins, the action of Hirudin is totally independent from any coagulation cofactor that may interfere or alter its action.⁵

Thrombexx is useful in the prevention of thromboembolic complications in at risk patients thrombexx (15 mg) is administered by subcutaneous injection 5-15 minutes before orthopedic or general surgery (after induction of regional block anesthesia) then 15 mg twice daily for 9-12 days and in bedridden patients until patient is fully ambulant (maximum 12 days)⁵

According to the FDA Therapeutic Equivalence Evaluation, 30th Edition, the biosimilar of recombinant hirudin, Desirudin is FDA approved, therefore, the same applies to recombinant hirudin in Egypt.

4.2. Correlative studies:

- 1- Study of Prevention of Thromboembolic with Use of Recombinant Hirudin, Results of a Double-Blind, Multicenter Trial Comparing the Efficacy of Desirudin (Revasc) with That of Unfractionated Heparin in Patients Having a Total Hip Replacement⁶ which showed that desirudin to be more effective than heparin in the prevention of deep vein thrombosis, without any increase in the requirements for transfusion or the risk of hemorrhage. The prevalences of over-all and proximal deep-vein thrombosis in the 174 patients who had been managed with desirudin and were included in the per-protocol analysis were 7 and 3 per cent (thirteen and six patients), respectively.⁶
- 2- Multicenter Trial of Desirudin for the Prophylaxis of Thrombosis: An Alternative to Heparin-Based Anticoagulation (DESIR-ABLE) shows that no patients experienced primary endpoints which is major bleeding and no new onset of symptomatic thrombosis requiring medical or surgical intervention or death.⁷

4.3. Study Rationale

The purpose of this study is to conduct several investigations required to evaluate the efficacy and safety of subcutaneous Thrombexx ampoules in the prophylaxis of Deep Vein Thrombosis (DVT) post major orthopedic operations

5. STUDY OBJECTIVES

5.1. Primary Objectives

To evaluate the efficacy of Subcutaneous Thrombexx® ampoules (r-Hirudin RB variant 15 mg) in DVT prophylaxis post major orthopedic operations

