6. TRIAL DESIGN

A Prospective, Single- Center, Phase IV Interventional, Single Arm conducted in Egypt to assess the efficacy and safety of patients undergoing major orthopedic operations such as Total knee & hip Arthroplasty with complete data and who had 2 weeks' follow-up.

This study will be conducted through main phases, preoperative phase which will be as a screening visit, operative phase which is the surgery will be done and a total of 3 follow-up visits which is the postoperative phase.

- 1- Pre-operative phase
- 2- Operative phase
- 3- Post operative phase (follow-up)

Detailed descriptions of the study design are as follows:

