8. STUDY OUTCOME MEASURES

8.1. Primary Endpoints

Primary end points included new onset symptomatic thrombosis requiring medical or surgical intervention or death due to thrombosis defined as fatal PE, ischemic

Sponsor: Minapharm Pharmaceuticals
Protocol Number: Sub-Thromb-001
Version: 1 amendment 1

stroke, mesenteric thrombosis, or myocardial infarction.

The number of clinical PE events will be measured by spiral CT

Mean changes in APTT where it will be done before first dose, 4 & 8 hours after first dose then on days 1,8,15 post operatively

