17. STATISTICAL METHODOLOGY

17.1. Determination of Sample Size

Sample size: Records for 100 patients who underwent major orthopedic surgery collected from 1 site

The sample size is based on literature review for previous studies, and a sample of 168 patients will be sufficient to detect an incidence of 12.5% of DVT with an acceptable error of 5%, and a 95% confidence level

17.2. Analysis Variables:

17.2.1. Primary analysis variables:

Proportion of patients experienced new onset symptomatic thrombosis
The number of clinical PE (Pulmonary Embolism) events will be measured by spiral CT

17.2.2. Secondary analysis variables:

Number of adverse events recorded
Proportion of patients experienced major bleeding

17.2.3. Statistical Method:

Descriptive analysis:

All statistical tests used a significance level of $P=0.05$, two tailed tests were performed for all analyses used statistical testing.

Descriptive analysis for quantitative data will include count, mean with 95% CI, standard deviation, median, minimum and maximum. For qualitative categorical variables; frequency and percentage and 95% confidence interval will be applied.

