8.2 Analyses variables

8.2.1 Primary analysis variables:

- Proportion of patients experienced new onset symptomatic thrombosis
- The number of clinical PE (Pulmonary Embolism) events will be measured by spiral CT

8.2.2 Secondary analysis variables:

- Number of adverse events recorded
- Proportion of patients experienced major bleeding

8.2.3 Statistical Method:

Descriptive analysis:

All statistical tests used a significance level of $P=0.05$, two tailed tests were performed for all analyses used statistical testing.

Descriptive analysis for quantitative data will include count, mean with 95% CI, standard deviation, median, minimum and maximum. For qualitative categorical variables; frequency and percentage and 95% confidence interval will be applied.

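### A single-arm trial with no reference rate and no decision rule can estimate an incidence of thrombosis but cannot support its stated efficacy objective, and its thrombosis outcome is defined inconsistently

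*Protocol*

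**What the plan says.** Protocol 5.1 and SAP 3.1 give the primary objective as "To evaluate the efficacy of Subcutaneous Thrombexx® ampoules (r-Hirudin RB variant 15 mg) in DVT prophylaxis post major orthopedic operations". Protocol 6 describes the design as "A Prospective, Single- Center, Phase IV Interventional, Single Arm conducted in Egypt to assess the efficacy and safety". The statistical method (Protocol 17.2.3, SAP 8.2.3) is descriptive: frequencies, percentages and 95% CIs for categorical variables, with a general statement that any tests are two-sided at 0.05. No control group, historical rate, performance goal, margin or success rule appears in either document.

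Thrombosis is described in three ways:

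- **Sample size** (Protocol 17.1, SAP 8.1): the planning value is an incidence of DVT, "sufficient to detect an incidence of 12.5% of DVT with an acceptable error of 5%, and a 95% confidence level". It is not limited to symptomatic cases, and its source is not named.
- **Endpoint** (Protocol 8.1, SAP 4.1): "Primary end points included new onset symptomatic thrombosis requiring medical or surgical intervention or death due to thrombosis", with the deaths including fatal PE, stroke, mesenteric thrombosis and myocardial infarction. The matching analysis variable in SAP 8.2.1 is "Proportion of patients experienced new onset symptomatic thrombosis".
- **Primary table** (SAP Table 8): titled as symptomatic thrombosis, but its rows cover whether the routine bilateral Doppler was done, whether it was read and signed, and whether it was normal or abnormal. It has no row for symptoms, intervention or death.

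Protocol 4.2 cites two desirudin studies. The first, in total hip replacement, is reported as "The prevalences of over-all and proximal deep-vein thrombosis in the 174 patients who had been managed with desirudin": 7% overall and 3% proximal (13 and 6 patients), per-protocol. The second reports "no new onset of symptomatic thrombosis requiring medical or surgical intervention or death", with no denominator.

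**The concern.** With no concurrent control, efficacy can only be inferred by setting the observed rate beside one from elsewhere. The plan does not say which rate, for which outcome, or what result would count as success. Those choices would be made after the data are seen.

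The non-zero thrombosis rates in the documents are DVT rates, whereas the written endpoint counts symptomatic events and thrombotic deaths. Routine Doppler in every patient can find DVT that causes no symptoms, so the two outcomes can differ widely in frequency. If the symptomatic proportion were read against a DVT rate, a low figure could be taken as a drug effect when it only reflects a narrower outcome. Because Table 8 tabulates Doppler findings under a symptomatic title, it is not even settled which proportion will be reported as the primary result.

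**Working it through.** **1. The plan's own figure.** Protocol 17.1 gives p = 0.125, error d = 0.05 and 95% confidence.

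n = z² p(1 − p) / d² = 1.96² × 0.125 × 0.875 / 0.05² = 168.06

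The stated 168 is reproduced. It is a precision calculation for estimating a DVT incidence. It is neither a test against a reference nor a calculation for the symptomatic endpoint. (At the 100 patients also stated there, the half-width is 1.96 × √(0.125 × 0.875 / 100) = 6.5 points. The conflict between 100 and 168 is a separate matter.)

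**2. Event counts that put the CI below an outside rate.** Exact (Clopper-Pearson) 95% CIs at N = 100:

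- Against 12.5%: 5 events give 1.6% to 11.3% (wholly below); 6 events give 2.2% to 12.6% (not). The limit is 5 or fewer.
- Against 7%: 1 event gives 0.03% to 5.4% (wholly below); 2 events give 0.2% to 7.04% (not). The limit is 1 or fewer.

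**3. How often an ineffective drug would do this.** The documents give no symptomatic rate for patients without effective prophylaxis, so a range of 1% to 5% is assumed. With X ~ Binomial(100, π), the columns are P(X ≤ 5), P(X ≤ 1) and P(X ≤ 6):

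| Assumed π | CI wholly below 12.5% | CI wholly below 7% | Point estimate below 7% |
|---|---|---|---|
| 1% | 99.9% | 73.6% | 99.99% |
| 2% | 98.5% | 40.3% | 99.6% |
| 3% | 91.9% | 19.5% | 96.9% |
| 4% | 78.8% | 8.7% | 89.4% |
| 5% | 61.6% | 3.7% | 76.6% |

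**4. The same calculation with matched outcomes.** If the trial counted the same outcome as the planning rate and the true value were 12.5%, P(X ≤ 5) = 1.1%. The high percentages in the 12.5% column therefore come from the unlike outcomes, not from any property of the drug.

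**5. Single results.** 3/100 has CI 0.6% to 8.5%, with exact two-sided p = 0.002 against 12.5% but p = 0.17 against 7%. For contrast, 10/100, as a Doppler DVT count might be, has CI 4.9% to 17.6% and p = 0.55 against 12.5%.

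**The case against.** The strongest reply is that the plan makes no such comparison. The 12.5% is only a planning value and the 7% only background; neither is called a benchmark, and the analysis is descriptive. That stands. A reader might infer that the trial will be judged against 12.5% or 7%, but the documents do not say so. What remains is an efficacy objective with nothing to read it against, and Protocol 18.6 commits to publishing or posting the results.

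Four further points limit what can be said.

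- It is tempting to say that the symptomatic rate must be lower than a DVT rate by definition. It need not be: the endpoint is not a subset of DVT, since it covers thrombosis at any site and thrombotic death. A lower rate is plausible, not guaranteed.
- It is tempting to say that the result would look like efficacy against either rate whatever the drug does. For 7% this fails: unless the assumed rate is near 1%, the CI usually includes 7%. That figure is also an active-drug, hip-only, per-protocol rate, while this trial takes hip and knee patients.
- If the abnormal Dopplers in Table 8 are reported as the primary result, the outcome is close to all DVT and the mismatch with 12.5% shrinks. The missing control and reference remain, and the table then contradicts its own title.
- The second cited study has a matching outcome, but without a denominator it gives no usable rate, and its patients also received drug.

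A reader might also suspect unrecorded mechanical prophylaxis. The documents do not say whether it is used, and the CRF is not among them, so nothing is claimed on that.

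A single arm is a legitimate Phase IV choice. The point concerns the claim made from it, not the lack of a second arm.

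**Conclusion.** The point holds as a mismatch between objective and design. Followed exactly, the plan yields an incidence with a confidence interval and no basis for an efficacy conclusion. It also leaves open which thrombosis outcome is primary, because the sample-size text, the endpoint and Table 8 disagree.

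The size of the risk is conditional on someone setting the symptomatic proportion beside a DVT rate, and on the assumed 1% to 5% symptomatic rate under an ineffective drug. On those terms the false impression is strong against 12.5% (whole CI below in 99.9% down to 62% of trials) and much weaker against 7% (74% down to 4%), although the point estimate alone would fall below 7% in 77% or more. Reading 12.5% as DVT of any kind follows the plain wording of Protocol 17.1, but its source is not given. The data remain usable; the conclusion drawn from them is what needs limiting.

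**What to change.** 1. Restate Protocol 5.1 and SAP 3.1 as estimating the 15-day incidence of thrombosis in patients given Thrombexx. Add that the single-arm result supports no claim of efficacy over another prophylaxis or over none.
2. Report two separate proportions, each with an exact 95% CI: all Doppler-detected DVT by day 15, and symptomatic thrombosis requiring intervention or thrombotic death.
3. Correct SAP Table 8 so that each proportion has its own rows, with symptoms, intervention and death shown for the second.
4. State that 12.5% and 7% may be set only beside the all-DVT proportion, descriptively and with differences in population and detection noted (including that the source of 12.5% is not given), and never beside the symptomatic rate.

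The cost is wording and table rows. Routine Doppler is already scheduled on days 1, 8 and 15, so no patients or procedures are added. The downside for the sponsor is a more modest claim.

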5.2. Secondary objectives

To evaluate the safety of Subcutaneous Thrombexx® ampoules (r-Hirudin RB variant 15 mg) in DVT prophylaxis post major orthopedic operations in terms of serious bleeding. Predictive factors; baseline characteristics, Thrombexx® dose, duration and concomitant medications.

Study population demographics and characteristics.

6. TRIAL DESIGN

A Prospective, Single- Center, Phase IV Interventional, Single Arm conducted in Egypt to assess the efficacy and safety of patients undergoing major orthopedic operations such as Total knee & hip Arthroplasty with complete data and who had 2 weeks' follow-up.

This study will be conducted through main phases, preoperative phase which will be as a screening visit, operative phase which is the surgery will be done and a total of 3 follow-up visits which is the postoperative phase.

- 1- Pre-operative phase
- 2- Operative phase
- 3- Post operative phase (follow-up)

Detailed descriptions of the study design are as follows:

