Title Page

A Prospective, Single- Center, Phase IV Interventional, Single Arm **T**rial for the
Evaluation of subcutaneous recombinant **H**irudin 15 mg (RB variant) in
prophylaxis of Deep Vein Thrombosis (**DVT**) post major orthopedic operations

Principle Investigator: [name]

Sub Investigator: [name]

Study Site: Alexandria University

Protocol Name: THRIVE-DVT

Protocol Number: Sub-Thromb-001

Version:1.0, amendment 1

Date: 25th of January, 2022

CONFIDENTIALITY STATEMENT

This study was performed in compliance with Good Clinical Practice (GCP), including the archiving of essential documents. This report has been prepared in accordance with ICH Harmonized Tripartite Guideline on the Structure and Content of Clinical Study Reports, dated November 1995.

Any and all information presented in this document shall be treated as confidential and shall remain the exclusive property of **Minapharm Pharmaceuticals** (or any of its affiliated companies). The use of such confidential information must be restricted to the recipients for the agreed purpose and must be disclosed, published or otherwise communicated to any unauthorized persons, for any reasons, in any form whatsoever without the prior written consent of **Minapharm Pharmaceuticals** (or the concerned affiliate company); "Affiliate Company" means any corporation, partnership or other entity which at the date of communication or afterwards with **Minapharm Pharmaceuticals**

1. Synopsis

Title	Description
Study Title	Prospective, Single- Center, Interventional, Single Arm Trial for the Evaluation of subcutaneous recombinant Hirudin 15 mg (RB variant) in prophylaxis of Deep Vein Thrombosis (DVT) post major orthopedic operations
Study number	Sub-Thromb-001
Study Phase	Phase IV
Study Design	Prospective, Single arm, single-center
Study population	Patients undergoing major orthopedic operations
Study procedures	
Drug: r-Hirudin Other Name: Thrombexx
 
100 Patients will be treated with r-Hirudin (Thrombexx) for a total of 15 days beginning with 15 mg BID s.c starting 6 hours after surgery or upon adequate hemostasis and continued until end of study.

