1.2 Study Rationale

The purpose of this study is to conduct several investigations required to evaluate the efficacy and safety of subcutaneous Thrombexx ampoules in the prophylaxis of Deep Vein Thrombosis (DVT) post major orthopedic operations

2 Study Design

A Prospective, Single- Center, Phase IV Interventional, Single Arm conducted in Egypt to assess the efficacy and safety of patients undergoing major orthopedic operations such as Total knee & hip Arthroplasty with complete data and who had 2 weeks follow-up.

This study will be conducted through main phases, preoperative phase which will be as a screening visit, operative phase which is the surgery will be done and a total of 3 follow-up visits which is the postoperative phase.

1. Pre-operative phase
2. Operative phase
3. Post-operative phase (follow-up)

Detailed descriptions of the study design are as follows:

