9.2 Primary End Point

Table 8 *Proportion of patients experienced new onset symptomatic thrombosis*

		Follow-up 1 (Day 1)	Follow-up 2 (Day 8)	Follow-up 3/ End of Study (Day 15)	p-value
Was a Routine bilateral compression Doppler done?	Yes, N (%)				
	No, N (%)				
If “No”, please indicate a reason	Reason 1, N (%)				
	Reason 2, N (%)				
	Reason 3, N (%)				
Is the report interpreted, signed & dated by the PI or any of the designated site staff?	(Yes), N (%)				
	(No), N (%)				
If “No”, please indicate a reason:	Reason 1, N (%)				
	Reason 2, N (%)				
	Reason 3, N (%)				
If “Yes”, the report interpretation shows that the subject is:	Normal, N (%)				
	Abnormal, N (%)				
If abnormal, please state the reason:	Reason 1, N (%)				
	Reason 2, N (%)				
	Reason 3, N (%)				

Table 9 *The number of clinical PE (Pulmonary Embolism) events will be measured by spiral CT*

		Follow-up 1 (Day 1)	Follow-up 2 (Day 8)	Follow-up 3/ End of Study (Day 15)	p-value
Was a Spiral CT done?	Yes, N (%)				
	No, N (%)				
If “No”, please indicate a reason	Reason 1, N (%)				
	Reason 2, N (%)				
	Reason 3, N (%)				
Is the report interpreted, signed & dated by the PI or any of the designated site staff?	(Yes), N (%)				
	(No), N (%)				
If “No”, please indicate a reason:	Reason 1, N (%)				
	Reason 2, N (%)				
	Reason 3, N (%)				
If “Yes”, the report interpretation shows that the subject is:	Normal, N (%)				
	Abnormal, N (%)				
If abnormal, please state the reason:	Reason 1, N (%)				
	Reason 2, N (%)				
	Reason 3, N (%)				

Table 10 *Mean changes in Activated Partial Thromboplastin Time (APTT) where it will be done before first dose, 4 & 8 hours after first dose then on days 1,8,15 post operatively*

		Before 1 st dose	After 1 st dose		Post-operative			p- value
			4 h	8 h	Day 1	Day 8	Day 15	
Was an APTT test performed?	Yes, N (%)							
	No, N (%)							
If “No”, please indicate a reason	Reason 1, N (%)							
	Reason 2, N (%)							
	Reason 3, N (%)							
If “Yes”, the test result is	APTT; Mean ± SD (sec)							
APTT, % change								
p-value								
The test interpretation shows that the subject is:	Normal, N (%)							
	Abnormal, N (%)							
If abnormal, please state the reason:	Reason 1, N (%)							
	Reason 2, N (%)							
	Reason 3, N (%)							

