9.4 Study Discontinuation

Table 20 Number and percent of causes of treatment discontinuations

		N = 100	p-value
Did the patient complete the study as per protocol?	Yes, N (%)		
	No, N (%)		
Reason for the discontinuation from study	Patient Withdrew Voluntarily		
	Adverse Event		
	Lost Follow-up		
	Death		
	Other Reasons		

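### The primary tables can miss thrombotic deaths that the endpoint counts, and no text sets the denominator of the primary proportion

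*Protocol*

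**What the plan says.** **Endpoint.** Protocol 8.1, repeated in SAP 4.1, defines the primary event as "new onset symptomatic thrombosis requiring medical or surgical intervention or death due to thrombosis defined as fatal PE", and then lists ischemic stroke, mesenteric thrombosis and myocardial infarction.

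**Analysis variable.** Protocol 17.2.1 and SAP 8.2.1 give two primary variables: "Proportion of patients experienced new onset symptomatic thrombosis", and the number of clinical PE events by spiral CT. Neither mentions death, and neither says which patients form the denominator. Categorical results get a frequency, a percentage and a 95% confidence interval.

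**Tables.** SAP Table 8 carries the title of the first variable and opens with "Was a Routine bilateral compression Doppler done". Its other rows record why a scan was not done, whether the report was signed, and whether it was normal or abnormal. Table 9 does the same after "Was a Spiral CT done". Both have columns for Day 1, Day 8 and Day 15. Neither has an N, a row for death, stroke, mesenteric thrombosis or infarction, or a row that counts each patient once over the whole period.

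**Who is analysed.** Protocol 6 describes assessing "patients undergoing major orthopedic operations such as Total knee & hip Arthroplasty with complete data and who had 2 weeks' follow-up". SAP 2 has the same phrase, "with complete data and who had 2 weeks follow-up". The synopsis, by contrast, says "100 Patients will be treated with r-Hirudin (Thrombexx". SAP Table 20, headed N = 100, lists death and loss to follow-up under "Reason for the discontinuation from study". No section of either document names an analysis set.

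**The concern.** The trial has one arm, and its main result is a single proportion with its interval. Someone who follows the SAP as written cannot produce the endpoint in 8.1, because the death component has no place in the variable or in the tables. The denominator is also open, so it could be chosen after the data are seen. Each gap can remove the gravest kind of primary event, an early fatal PE, from the headline figure. The missing denominator affects major bleeding in the same way: Table 11 has no N either, and a patient who dies early of a bleed does not have two weeks of follow-up.

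**Working it through.** **1. The plan's own figure.** The only calculated number is the 168 patients in protocol 17.1: 1.96² × 0.125 × 0.875 / 0.05² = 168.07, which reproduces it. It concerns the incidence of DVT. It gives no expected rate for the 8.1 composite or for fatal PE, so the counts below are assumptions.

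**2. Endpoint against tables.**

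| Component in 8.1 | Named in 17.2.1 / SAP 8.2.1 | Place in Tables 8-9 |
|---|---|---|
| Symptomatic DVT | yes, as symptomatic thrombosis | Doppler, normal or abnormal, by visit |
| PE with a CT | yes, as a count | CT, normal or abnormal, by visit |
| Fatal PE without a CT | no | none |
| Stroke, mesenteric thrombosis, infarction | not by name | none |
| Any event, each patient once | no | none |

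The visit columns cannot simply be added, because one patient may be abnormal at two visits.

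**3. Are the data collected?** Protocol 16.1 records adverse events to the patient's end of study, and 16.2 collects serious adverse events to the end of follow-up. Neither is tied to dosing. The missing components should therefore be available from the SAE data.

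**4. Size, on assumed counts.** The documents do not name an interval method; the exact (Clopper-Pearson) interval is used here. For x events in n patients, the lower limit is the 2.5% point of Beta(x, n − x + 1) and the upper limit is the 97.5% point of Beta(x + 1, n − x). With x = 0 the upper limit is 1 − 0.025^(1/n): 3.62% for n = 100 and 3.66% for n = 99. Every fatal PE below is assumed to have no CT entered in Table 9.

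| Assumed events among 100 dosed | All 8.1 events, all dosed | Tables as drawn, all 100 | Completers reading |
|---|---|---|---|
| None, all complete | 0/100 (0-3.62%) | 0/100 (0-3.62%) | 0/100 (0-3.62%) |
| 1 fatal PE | 1/100 = 1.00% (0.03-5.45%) | 0/100 (0-3.62%) | 0/99 (0-3.66%) |
| 1 fatal PE, 10 other non-completers | 1/100 = 1.00% (0.03-5.45%) | 0/100 (0-3.62%) | 0/89 (0-4.06%) |
| 2 fatal PEs | 2/100 = 2.00% (0.24-7.04%) | 0/100 (0-3.62%) | 0/98 (0-3.69%) |
| 2 fatal PEs, 2 imaged events in completers | 4/100 = 4.00% (1.10-9.93%) | 2/100 = 2.00% (0.24-7.04%) | 2/98 = 2.04% (0.25-7.18%) |

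The last column stays the same if a composite row is added but the completers reading is kept, because the patients who died have left the set. Repairing one gap therefore does not recover the event. Each lost event costs about one percentage point.

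**The case against.** **The phrase in protocol 6 is not an analysis rule.** It stands in a design description and appears in neither the eligibility criteria nor the statistical sections. The synopsis plans to treat 100 patients, Tables 8 to 10 have rows for tests not done, and Table 20 counts deaths and losses within N = 100. A reader might infer that the plan excludes early deaths. The documents do not support that; they support only that the set is unnamed and that one phrase conflicts with the rest.

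**A fatal PE need not be lost.** The synopsis has clinical PE confirmed by spiral CT, so a patient scanned before death could be entered as abnormal in Table 9. A reader might infer that every thrombotic death disappears, or that it would be seen only among the SAEs. Neither follows. The loss arises when no scan is tabulated, and Table 20 also has a row for death. The event can be missing from the primary result without being missing from the report.

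**The direction is not all one way.** Table 8 is titled for symptomatic thrombosis but tabulates routine Doppler results, so a finding without symptoms could raise the reported rate. That is fair, and it means the net bias is unknown. It does not restore the omitted components.

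**The counts are assumed.** The protocol's own summary of an earlier desirudin trial (4.2) reports no primary events. If that recurs here, the gaps have no effect on the estimate. This stands, and it is why the point is not graded higher.

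None of these answers the mismatch in step 2, which holds however protocol 6 is read.

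**Conclusion.** The point holds, as something that should be fixed. The primary variable and Tables 8 and 9 do not cover the endpoint in 8.1, and the denominator is not stated. A thrombotic death without a tabulated scan, or a stroke, mesenteric thrombosis or infarction, can be absent from the primary proportion. On the assumption of one such death in 100, the result is 0% instead of 1.0%, and the upper limit is about 3.6 to 3.7% instead of 5.45%. With none, there is no difference. No success threshold is set, so no stated decision would change.

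One ambiguity has to be settled first. The list in 8.1 can be read as defining thrombotic death, so that stroke, mesenteric thrombosis and infarction count only when fatal, or as naming separate events that count in any case. This review does not choose between the readings. Fatal cases count under both.

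**What to change.** - **Variable and table.** Amend protocol 17.2.1 and SAP 8.2.1 so that the primary variable is the proportion of patients with any 8.1 event through Day 15. Add to the primary tables one cumulative row, with N, that counts each patient once and is filled from the SAE data as well as the scans.
- **Definition.** State in 8.1 and SAP 4.1 whether stroke, mesenteric thrombosis and infarction count only when fatal or also when non-fatal.
- **Denominator.** Delete the completers phrase from protocol 6 and SAP 2. Use all patients who received at least one dose, for both the primary endpoint and major bleeding.
- **Follow-up.** State that stopping the drug does not end the Day 8 and Day 15 assessments. DVT, PE and major bleeding are listed stopping rules in the synopsis, and nothing now says what happens to later visits.

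The cost is a small amendment with sponsor authorisation and IRB/IEC approval (protocol 15.2), matching SAP text, and a check that the CRF's SAE pages identify these events. No new visits are needed. The downsides are some follow-up work for patients who have stopped the drug and a possibly less favourable event rate.
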